This class of drugs has not been tested specifically in subjects with DBA prior to this study. To mitigate the potential risks of administering TFP to this new population, we will (1) start dosing at dose levels well below those prescribed for psychosis over the past several decades, (2) dose escalate to a maximum of 10 mg daily (the lowest dose typically prescribed for psychosis), and (3) perform weekly safety monitoring. Given the positive signal in DBA animal models and the 60-year clinical experience with higher doses of TFP, this drug warrants a trial in humans to assess tolerability in DBA. If tolerated, this trial will support either a PoC trial of low-dose TFP in DBA, or the advancement of a chemically modified TFP-like drug (to alleviate the neurologic toxicity) for the treatment of DBA.

This is a dose escalation safety and tolerability study to evaluate the presence of TFP-related adverse events in DBA subjects, and to determine the maximum tolerated dose (MTD) of TFP in DBA. The dose escalation strategy is described in [Section 3.5 Dose Rationale and Risk/Benefits](#).

Some first-in-human (FIH) trials may implement an enrollment restriction rule such that two subjects are dosed in a given cohort, and a third subject is not dosed until both of the first two subjects have demonstrated tolerability. For this trial, we have elected not to use such an enrollment restriction design for the following reasons:

- a. This is not a FIH trial: TFP has been in wide clinical use for 60 years.
- b. Our dose levels (1 mg daily, up to max 10 mg daily) are all well within and below the safe range of clinical use. Doses in the 2-6 mg daily range have been shown to have a side effect profile similar to placebo in patients with anxiety ([Mendels, 1986](#)). A randomized clinical trial comparing TFP 15 mg/day vs. placebo in schizophrenic subjects revealed no difference in the rates of severe adverse effects, Parkinsonism or dystonia compared to placebo (Koch, 2014). Doses for psychosis range from 10 mg daily up to 40-50 mg daily, whereas we will dose at 1, 2, 5, and 10 mg daily only.

- c. We will monitor for safety, specifically for any hematologic toxicity and for extrapyramidal/central nervous system (CNS) effects. Dose escalation criteria and actions, as well as subject and cohort stopping rules are detailed in [Section 6 Study Design](#).

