## **7.5 Consent Process**

Informed consent will be obtained by the study PI or authorized co-investigators after they have fully explained the study. The study will be presented to all eligible subjects and explained in terms that are appropriate for each subject. After a full discussion and the

opportunity to ask questions, subjects will be consented. The subject may take as much time as needed to decide on his/her participation in the study, and may consent after the initial contact is made. The consent will be obtained either in the outpatient area at a regular office visit or via mail, after the study is discussed on a telephone call.

The subjects with DBA who may be eligible for this study may live in any state in the United States. Since travel may be difficult, it is often necessary to screen the subject for eligibility before they travel for the study. Therefore the consent is mailed to the subject. Once the subject has the consent in hand, the consent will be reviewed with him/her over the phone in its entirety. Questions can be asked and answered and the subject can determine the appropriateness of the study for him/herself. Once consent is signed and received by the PI, then the screening procedure can begin. Eligibility can therefore be determined prior to the subject's travel and confirmed upon subject's arrival to the office visit. A standard informed consent form will be utilized for this study. Subjects may have family members, their local physicians and any other chosen individuals review the consent with them prior to their signing. For subjects who sign consent remotely, the study PI or authorized co-investigator will review the study and the consent form again when the subject comes for the in-person physical examination and to begin the study. At that time an enrollment note will document the continued willingness of the subject to participate in the study.

The study is 4 weeks in duration and subjects may withdraw their consent at any time. Subjects will be seen weekly for the actual study drug timeframe of the study and will be given the opportunity to withdraw consent at any time.

This study does not involve subjects less than 18 years of age.

This study does not involve cognitively impaired adults.

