### **8.9.3 Dispensing of Study Drug**

The subject will be dispensed a 21 day supply of 1 mg or 5 mg tablets based on Dose Level 1, 2, or 3 and 4, respectively. The subject will receive study drug once during this study.

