## **9.3 Visit 2**

Visit 2 will be Day 11 ( $\pm$  1 day) of the study. The subject will undergo full safety analysis, including a physical examination (including weight, vital signs, blood pressure and neurological exam). Karnofsky performance status will be assessed. Blood work will be performed for a complete blood count (CBC; RBC count, hemoglobin, hematocrit, absolute reticulocyte count, white blood cell count, absolute neutrophil count, and platelet count), serum chemistry panel for hepatic and renal function (blood urea nitrogen, creatinine, bilirubin [total and direct], aspartate aminotransferase [AST], and alanine aminotransferase [ALT]), and

pharmacodynamic marker analysis, if applicable (Appendix J). If the subject is a female, menstrual status will be assessed and a serum pregnancy test will also be performed. Transfusion history will be documented. The subject will be questioned and evaluated for any adverse events. All concomitant therapies will be documented.

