#### **9.4 Visit 3**

Visit 3 will be Day 22 ( $\pm 2$  days) of the study. The subject will undergo full safety analysis, including a physical examination (including weight, vital signs, blood pressure and neurological exam). Karnofsky performance status will be assessed. Blood work will be performed for a complete blood count (CBC; RBC count, hemoglobin, hematocrit, absolute reticulocyte count, white blood cell count, absolute neutrophil count, and platelet count), serum chemistry panel for hepatic and renal function (blood urea nitrogen, creatinine, bilirubin [total and direct], aspartate aminotransferase [AST], and alanine aminotransferase [ALT]), and pharmacodynamic marker analysis, if applicable (Appendix J). If the subject is a female, menstrual status will be assessed. Transfusion history will be documented. The subject will be questioned and evaluated for any adverse events. All concomitant therapies will be documented.

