## 10 Risks to Subjects

Adverse reactions with TFP include drowsiness, dizziness, skin reactions, rash, dry mouth, insomnia, amenorrhea, fatigue, muscular weakness, anorexia, lactation, blurred vision, and neuromuscular (extrapyramidal) reactions. Details regarding extrapyramidal and other adverse reactions with TFP follow:

- **Neuromuscular (Extrapyramidal) Reactions:** These symptoms are characterized by motor restlessness. They may be of the dystonic type, or they may resemble Parkinsonism (described below).
- **Motor Restlessness:** Symptoms may include agitation or jitteriness and sometimes insomnia. These symptoms often disappear spontaneously.
- **Dystonia (Class Effect):** Symptoms of dystonia, prolonged abnormal contractions of muscle groups, may occur in susceptible individuals during the first few days of treatment. Dystonic symptoms include spasm of the neck muscles, sometimes progressing to tightness of the throat, swallowing difficulty, difficulty breathing, and/or protrusion of the tongue. While these symptoms can occur at low doses, they occur more frequently at higher doses of first generation antipsychotic drugs.
- **Pseudoparkinsonism:** Symptoms may include mask-like facies, drooling, tremors, pill-rolling motion, cogwheel rigidity, and shuffling gait.
- **Tardive Dyskinesia:** Tardive dyskinesia is a rare syndrome characterized by rhythmical involuntary movements of the tongue, face, mouth, or jaw (e.g., protrusion of tongue, puffing of cheeks, puckering of mouth, chewing movements). These symptoms may be accompanied by involuntary movements of extremities. In rare instances, these involuntary movements of the extremities are the only manifestations of tardive dyskinesia. Symptoms may persist for months or years and, while they gradually disappear in some subjects, they may be irreversible in others. The risk appears to be greatest in elderly subjects (especially women) on prolonged, high-dose therapy. There is no known effective treatment for tardive dyskinesia. It has been reported that fine vermicular movements of the tongue may be an early sign of the syndrome and if the medication is stopped at that time the syndrome may not develop.
- **Adverse Reactions Reported with TFP or Other Phenothiazine Derivatives:** Adverse effects with different phenothiazines vary in type, frequency, and mechanism of

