## 22.1 Appendix A continued

\*Historical clinical laboratory evaluations performed for medical evaluation within 28 days are acceptable for study entry.

- a: All Day 1 assessments are to be done prior to TFP administration. TFP should be initiated within 7 days following a blood transfusion.
- b: Hematology laboratory evaluations (RBC count, hemoglobin, hematocrit, absolute reticulocyte count, white blood cell count, absolute neutrophil count, and platelet count) will be collected at Screening and at subsequent visits during the Treatment and Follow-Up Periods, as referenced in the schedule above. Any laboratory evaluations may be repeated more frequently if clinically indicated.
- c: Serum chemistry laboratory evaluations (blood urea nitrogen, creatinine, bilirubin [total and direct], aspartate aminotransferase [AST], alanine aminotransferase [ALT]) will be collected at Screening and at subsequent visits during the Treatment and Follow-Up Periods, as referenced in the schedule above. Any laboratory evaluations may be repeated more frequently if clinically indicated.
- d: Blood for pharmacodynamic disease marker analysis will be shipped to supporting company (see Appendix F).
- e: Females of childbearing potential: A female of childbearing potential is a sexually mature woman who has not undergone a hysterectomy or who has not been postmenopausal for at least 24 consecutive months (i.e., who has had menses at some time in the preceding 24 months). A serum pregnancy test (which must be negative) must be performed not more than 3 days from the start of TFP administration (Study Day 1). Subjects must agree to use highly effective methods of birth control during study participation and for at least 1 week following the last dose of TFP. Subjects must be counseled concerning measures to be used to prevent pregnancy and potential toxicities prior to the first dose of TFP. Serum pregnancy tests will be performed according to the above schedule during study participation.
- f: Subjects must have documented transfusion history for > 12 weeks before inclusion/initiation of treatment.

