#### **Description of procedure**

The study is 29 days long and consists of taking the study drug TFP for 21 days and being monitored for an additional 8 days. The patient will have a total of 4 visits over the period of 29 days. A review of the patient's history, physical examination, and laboratory blood work will be

done in order to determine if the patient is eligible to participate. While the patient is taking the TFP, he or she will need to be seen at The Feinstein Institutes for Medical Research or the participating institution 3 times over the first 21 days and virtually for the last visit. During the first 21 days the patient will be taking TFP once a day, orally as a tablet, and will continue the red blood cell transfusions as routinely scheduled, every 3-4 weeks.

The following are some of the basic inclusion and exclusion criteria for this pilot trial.

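### Weekly monitoring on drug is stated but not scheduled, and, separately, no contact falls in the first days, when dystonia may appear

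*Combined protocol and SAP*

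**What the plan says.** Two places state a weekly frequency on drug. Section 2 lists three ways of limiting risk in a population new to this drug class, and the third is to "perform weekly safety monitoring". Section 7.5 says: "Subjects will be seen weekly for the actual study drug timeframe of the study".

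The operative schedule is different:

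- Appendix A, footnote a: "All Day 1 assessments are to be done prior to TFP administration". The Day 1 visit therefore yields no on-treatment information.
- Section 8.9.3: "The subject will receive study drug once during this study". No dispensing visit creates a further contact.
- Section 9.3: "Visit 2 will be Day 11", with a window of ±1 day.
- Section 9.4: "Visit 3 will be Day 22", with a window of ±2 days.
- Appendix A has no column between Visits 1 and 2 or between Visits 2 and 3.
- The study announcement (Appendix G) tells subjects they will be seen "3 times over the first 21 days and virtually for the last visit", which matches Section 9 and not the weekly statements.

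On timing of harm, Section 10 says that dystonia "may occur in susceptible individuals during the first few days of treatment", that it can occur at low doses, and that it sometimes progresses to throat tightness and difficulty breathing.

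**The concern.** There are two separate points.

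**The stated mitigation is not in the schedule.** Section 6.1 ties on-drug safety assessment to the required schedule, so sites will follow Section 9 and Appendix A. Section 2 also gives monitoring for hematologic and extrapyramidal/CNS effects as a reason for not staggering enrollment. A reader of Sections 2 or 7.5 would believe that subjects are checked more often than they will be.

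**The first contact-free stretch covers the days that Section 10 singles out for dystonia.** What could be lost is mild or short-lived early extrapyramidal symptoms. These matter because Section 15.4 lists such symptoms with no evident grade threshold. One affected subject stops treatment. Two or more in a cohort stop the study, with no MTD declared in Cohort A and the next lower dose declared in Cohorts B to D. An episode that is not volunteered and has resolved by Visit 2 reaches those rules only through recall.

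**Working it through.** **Inputs.** First dose on Day 1 (Section 9.2); Visit 2 on Day 11 ±1 (Section 9.3); Visit 3 on Day 22 ±2 (Section 9.4); 21 once-daily doses (Section 8.2). Intervals are counted from the day of the first dose.

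**Stated frequency against the schedule.** Weekly means an interval of 7 days, with contacts on Days 8, 15 and 22: three after the first dose. Two are scheduled.

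| Interval | Nominal | With windows |
|---|---|---|
| Day 1 to Visit 2 | 11 − 1 = 10 days | 10 − 1 = 9 to 12 − 1 = 11 |
| Visit 2 to Visit 3 | 22 − 11 = 11 days | 20 − 12 = 8 to 24 − 10 = 14 |

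Even the shortest possible interval exceeds 7 days, so the weekly figure is not reproduced.

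**Exposure before the first on-treatment question.** Counting doses before the one due on the visit day, Visit 2 on Day 10, 11 or 12 follows 9, 10 or 11 doses: 9/21 = 43%, 10/21 = 48%, 11/21 = 52%.

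**Would weekly contact cover the early days?** No. It would begin on Day 8, after the first few days. The early contact therefore has to be justified from Section 10, not from the weekly wording.

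**Effect of an early contact.** Section 10 attaches no number to the early period. As an assumption, take onset on Days 1 to 4.

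- Now: first question after 10 − 4 = 6 to 12 − 1 = 11 days, with 5 to 10 doses taken after the onset day.
- Contact on Day 5: first question after 5 − 4 = 1 to 5 − 1 = 4 days, with 0 to 3 such doses.
- Contact on Day 3: onset on Day 1 or 2 is asked about after 3 − 2 = 1 to 3 − 1 = 2 days. Onset on Day 4 still waits for Visit 2, 10 − 4 = 6 to 12 − 4 = 8 days.
- Limit of Day 5: onset on Days 5 to 7 after the contact gains nothing. It waits 10 − 7 = 3 to 12 − 5 = 7 days, with 2 to 6 doses, unless the subject reports it.

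**Intervals under the two options** (new contacts held on their nominal day).

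| Option | Nominal intervals on drug (days) | Longest with visit windows |
|---|---|---|
| Day 5 and Day 16 | 4, 6, 5, 6 | 24 − 16 = 8 |
| Day 5 only | 4, 6, 11 | 24 − 10 = 14 |

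If the new contacts carry ±1 day themselves, the longest interval in the first option is 24 − 15 = 9 days. The first option is about weekly. The second is not, so it requires the weekly statements to be withdrawn.

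**The case against.** The strongest reply is that the operative text agrees with itself. Section 9, Appendix A and the announcement match, and the weekly wording sits only in a summary and a consent narrative. On that view the defect needs two lines of correction and nothing more. This stands for the wording. It does not remove the timing point, which depends on Section 10.

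Second, the expected risk is low. Section 3.4 reports no difference from placebo in severe adverse effects, Parkinsonism or dystonia at 15 mg/day, above this trial's range, and a placebo-like profile at 2 to 6 mg/day. Section 3.5 expects extrapyramidal symptoms to be less likely at these doses, and exclusion 10 removes subjects with extrapyramidal history. Severe dystonia would probably be self-reported, and an event recalled at Visit 2 still counts, because Section 15.2 requires specific questioning at each contact. All of this stands. Call-in instructions may also exist in the consent pages, which are not available. They would not change Section 9 or Appendix A, which set the schedule.

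Third, a remote call supplies no blood count and no neurological examination, so it does not deliver the weekly monitoring that Section 2 implies. This stands, and is why Section 2 needs rewording as well as Section 7.5.

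Fourth, asking has a price. Restlessness, as Section 10 describes it, includes non-specific complaints that often resolve unaided. Soliciting them in an open-label trial without a control arm could stop a subject or the study under Section 15.4. This stands as a real downside of the remedy.

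A reader might infer that the weekly promise itself requires a Day 5 contact. It does not, as the Day 8 calculation shows.

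**Conclusion.** The point holds in limited form. Weekly monitoring is stated in Sections 2 and 7.5 and is not scheduled: the on-drug gaps are 9 to 11 and 8 to 14 days. Independently, no contact is scheduled in the early days that Section 10 names for dystonia, and 43% to 52% of doses precede the first on-treatment question. Both should be corrected, because safety is the primary objective and the plan relies on this monitoring as a mitigation.

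The figures are schedule facts, not effect estimates. The gain from an early contact assumes onset on Days 1 to 4. Any contact at about Day 3 to 5 would serve; Day 5 is a reasonable choice, not one derived from the documents. The timing argument covers dystonia only, since no onset time is given for restlessness or for akathisia.

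It would be tempting to conclude that dystonia will be missed or that the declared MTD will be too high. The documents do not support this. They give no rate for unreported early events, and Section 6.1 counts only toxicity of Grade 3 or worse, so mild events can bear on the outcome only through Section 15.4.

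**What to change.** **Preferred.** Add to Section 9 and Appendix A two remote adverse-event contacts by existing staff, one at about Day 3 to 5 (Day 5 is suggested) and one at about Day 16. Use video where possible; Section 9.5 already accepts it for the follow-up visit. Ask specifically about dystonia and restlessness since the last contact, and record the answers on the adverse-event page of the case report form. Reword Sections 2 and 7.5 to state adverse-event contact about weekly, with on-treatment blood work and neurological examination at Visits 2 and 3 only.

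**Minimum.** Correct Sections 2 and 7.5 to the actual schedule and add only the early contact.

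Either way, Visits 2 to 4 and the stopping rules stay as they are, and events are handled under the existing Sections 6.1 and 15.4.

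**Cost.** With at most 24 cohort places: 24 × 1 = 24 contacts for the minimum or 24 × 2 = 48 for the preferred option, one or two new columns in Appendix A, and an amendment. A telephone call gives no visual assessment. More mild extrapyramidal symptoms will be elicited, and the team should accept in advance that these could trigger a subject or study stop under Section 15.4.

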occurrence, i.e. some are dose-related, while others involve individual subject sensitivity. Some adverse effects may be more likely to occur, or occur with greater intensity, in subjects with special medical problems, e.g., subjects with mitral insufficiency or pheochromocytoma have experienced hypotension following recommended doses of certain phenothiazines.

- Neuroleptic malignant syndrome (NMS) has been reported in association with antipsychotic drugs. Cardinal features of NMS are hyperpyrexia, muscle rigidity, altered mental status (including catatonic signs), and evidence of autonomic instability (irregular pulse or blood pressure). Additional signs may include elevated creatine phosphokinase, myoglobinuria (rhabdomyolysis), and acute renal failure. NMS is potentially fatal and requires symptomatic treatment and immediate discontinuation of neuroleptic treatment.

- Not all of the following adverse reactions have been observed with every phenothiazine derivative, but they have been reported with one or more and should be borne in mind when drugs of this class are administered: extrapyramidal symptoms (opisthotonos, oculogyric crisis, hyperreflexia, dystonia, akathisia, dyskinesia, parkinsonism) some of which have lasted months and even years—particularly in elderly subjects with previous brain damage; grand mal and petit mal convulsions, particularly in subjects with electroencephalogram abnormalities or history of such disorders; altered cerebrospinal fluid proteins; cerebral edema; intensification and prolongation of the action of central nervous system depressants (opiates, analgesics, antihistamines, barbiturates, alcohol), atropine, heat, organophosphorus insecticides; autonomic reactions (dryness of mouth, nasal congestion, headache, nausea, constipation, obstipation, adynamic ileus, ejaculatory disorders/impotence, priapism, atonic colon, urinary retention, miosis and mydriasis); reactivation of psychotic processes, catatonic-like states; hypotension (sometimes fatal); cardiac arrest; blood dyscrasias (pancytopenia, thrombocytopenic purpura, leukopenia, agranulocytosis, eosinophilia, hemolytic anemia, aplastic anemia); liver damage (jaundice, biliary stasis); endocrine disturbances (hyperglycemia, hypoglycemia, glycosuria, lactation, galactorrhea, gynecomastia, menstrual irregularities, false-positive pregnancy tests); skin disorders (photosensitivity, itching, erythema, urticaria, eczema up to exfoliative

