dermatitis); other allergic reactions (asthma, laryngeal edema, angioneurotic edema, anaphylactoid reactions); peripheral edema; reversed epinephrine effect; hyperpyrexia; increased appetite; increased weight; a systemic lupus erythematosus-like syndrome; pigmentary retinopathy; with prolonged administration of substantial doses, skin pigmentation, epithelial keratopathy, and lenticular and corneal deposits.

- Electrocardiogram changes, particularly nonspecific, usually reversible Q and T wave distortions, have been observed in some subjects receiving phenothiazine antipsychotics.

There have been occasional reports of sudden death in subjects receiving phenothiazines. In some cases, the cause appeared to be cardiac arrest or asphyxia due to failure of the cough reflex.

The effects of TFP on fertility or a fetus are not known. The side effects of TFP on newborns are also not known, therefore breastfeeding will not be allowed on the study. The subject will be removed from the study if she becomes pregnant during the study.

Adult subjects with DBA who are on chronic transfusion therapy may have iron overload despite iron chelation or due to non-compliance. Iron overload can lead to liver dysfunction (liver function test elevations initially and eventual fibrosis and cirrhosis), cardiac dysfunction (arrhythmias and eventual heart failure), and endocrine dysfunction (hypothyroidism, diabetes mellitus, growth hormone deficiency, hypogonadism, premature ovarian failure, etc.). If such dysfunction is documented but is adequately addressed, then these subjects will be eligible for this study. If any of these potential side effects occur for the first time while on the subject is on the study drug, the event will be treated as an adverse event (AE).

Subjects with DBA have RBC aplasia, thus necessitating transfusion therapy. As this is a bone marrow failure syndrome these subjects also can have other cytopenias including neutropenia and thrombocytopenia, and often pancytopenia (not necessarily consistent with aplastic anemia). The eligibility criteria for entry into the study allow mild abnormalities in all the cell lines, but subjects with severe cytopenia are ineligible.

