## 22.1 Appendix A: Study Assessment Schedule

	Screening Period	Treatment Period			Follow-Up
	Screening	Visit 1	Visit 2	Visit 3	Visit 4
	Day -28 to Day -1	Day 1 a (±1d)	Day 11 (±1d)	Day 22 (±2d)	Day 29 (±2d)
Obtain subject informed consent form		-	-	-	-
Assess inclusion/exclusion criteria		-	-	-	-
Obtain medical subject history		-	-	-	-
Record prior treatments and procedures (including transfusion history)		-	-	-	-
Physical examination (including height at 1 st visit only, weight, vital signs, blood pressure and neurological examination)					
Karnofsky performance status (Appendix E)					-
Hematology b,*					
Blood chemistry, hepatic function, kidney function c,*					
Blood for pharmacodynamic disease marker analysis (Appendix J) d	-				-
Menstrual status					-
Pregnancy test e,*				-	-
Transfusion assessment f					
Adverse events	-				

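### Section 10 counts first-time diabetes and arrhythmia on drug as adverse events, but no visit schedules glucose or an ECG, so symptom-free cases are not systematically detected and have no measured pre-dose value

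*Combined protocol and SAP*

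**What the plan says.** Section 10 (Risks to Subjects) deals with these effects in two places.

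- **Population risk.** Chronically transfused subjects may carry iron overload. This can cause liver dysfunction, "cardiac dysfunction (arrhythmias and eventual heart failure), and endocrine dysfunction (hypothyroidism, diabetes mellitus" and other endocrine failures. Subjects whose dysfunction is documented and under control may enter. The section then gives a classification rule: "If any of these potential side effects occur for the first time while on the subject is on the study drug", it counts as an adverse event.
- **Drug risk.** A separate list of phenothiazine reactions includes "endocrine disturbances (hyperglycemia, hypoglycemia, glycosuria". It adds: "Electrocardiogram changes, particularly nonspecific, usually reversible Q and T wave distortions, have been observed" in some subjects on this class.

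Section 6.2 makes treatment-emergent adverse events a primary endpoint. Section 14.2 summarises the key laboratory results by CTCAE grade but does not say which results are key.

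The chemistry panel in Appendix A, footnote c, is "blood urea nitrogen, creatinine, bilirubin [total and direct], aspartate aminotransferase [AST], alanine aminotransferase [ALT". Sections 7.4 and 9.1 to 9.4 itemise the same analytes, and section 9.5 refers to the panel by name for Visit 4. The physical examination row of Appendix A covers "weight, vital signs, blood pressure and neurological examination". No row provides for an ECG.

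**The concern.** The protocol gives two independent reasons to expect glucose and rhythm effects, one from the disease and one from the drug class. It rules that a first occurrence of diabetes or arrhythmia on drug is an adverse event, but schedules no objective measurement of either, before or during treatment.

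Two things follow. A subject with raised glucose or an altered tracing and no symptoms passes through the study without the change being looked for. And if an unscheduled test does show something abnormal, there is no pre-dose value from the study with which to judge whether it is new.

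The stake is how the safety summary can be read. Section 2 notes that non-neurologic adverse effects have not been studied in this population. Section 10 says that, if no significant toxicity appears, the drug will be modified to stay out of the brain. Non-neurologic safety is then what the next compound would rely on. A table with no glucose or rhythm events could mean that none occurred, or only that none caused symptoms.

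**Working it through.** The plan gives no figure on this point, so the check sets what section 10 names against what sections 7.4, 9.1 to 9.5 and Appendix A schedule.

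| Named in section 10 | Scheduled measurement | Time points (of 5) | Measured pre-dose value |
|---|---|---|---|
| Liver dysfunction | AST, ALT, bilirubin | 5 | Yes, with entry limits in section 7.2 |
| Diabetes; high or low glucose; glycosuria | None (no glucose, HbA1c or urinalysis) | 0 | No |
| Arrhythmia; ECG changes | No ECG (vital signs only) | 0 | No tracing |

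The five time points are Screening and Visits 1, 2, 3 and 4. The liver row shows that the schedule can support the section 10 rule, and does so for one of the organ systems that the rule covers.

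**Is an undetected change one that the plan would count?** The answer differs for the two.

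- *Glucose.* Section 15.1 makes a laboratory abnormality an adverse event if any one of several conditions is met, including that a repeat test does not refute it or that it suggests disease. A symptom-free raised glucose can qualify, but only if it is measured.
- *ECG.* Section 15.1 makes an abnormal diagnostic result an adverse event only if it leads to withdrawal, accompanies a serious event or symptoms, prompts treatment or more tests, or is judged clinically significant. A symptom-free, nonspecific tracing change need not qualify.

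Glucose is therefore the stronger half of the point.

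**How many draws already exist?** Five if every time point has its own sample, and four if Screening and Visit 1 are combined, as section 9.1 allows. Section 14.1 states enrolment of 3 to 24, which reproduces as 1 × 3 = 3 and 4 × 6 = 24. If all subjects complete, that gives between 3 × 4 = 12 and 24 × 5 = 120 glucose results from existing samples.

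**Could the gap change escalation?** A cohort passes with 0 of 3 events, or with 1 of 3 followed by 0 of 3. With true Grade 3 or higher rate p and detected fraction d, put q = p × d:

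P(pass) = (1 − q)³ + 3q(1 − q)² × (1 − q)³

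| Assumed p | d = 1 | d = 0.5 | d = 0 |
|---|---|---|---|
| 0.10 | 0.906 | 0.973 | 1.0 |
| 0.20 | 0.709 | 0.906 | 1.0 |
| 0.30 | 0.494 | 0.814 | 1.0 |

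For example, p = 0.30 and d = 1 gives 0.343 + 3 × 0.3 × 0.49 × 0.343 = 0.494. Both p and d are assumptions, because the documents give neither. Many silent glucose or ECG changes would also fall below Grade 3. The table shows the direction that missed severe events would push the design. It does not estimate this trial's error.

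**The case against.** The strongest reply is that the protocol chose its targets. Section 2 directs monitoring to hematologic toxicity and to extrapyramidal and CNS effects, and the blood counts and neurological examinations follow from that. Doses are at most 10 mg a day for 21 days. A list of class risks is not a promise to test for each one: section 10 also names hypothyroidism, hypogonadism and retinopathy, and none has a dedicated test. The first-occurrence rule says how to classify an event that comes to light, not that every event will be sought. As a defence of the overall design, this stands.

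It also rules out stronger readings that a reader might infer:

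- *That these events are invisible.* They are not. Section 15.2 requires questioning at each contact and examination where appropriate. Appendix A schedules vital signs at every time point, although Visit 4 may be virtual. Section 15.1 allows other tests. Symptomatic diabetes or arrhythmia has a route into the data.
- *That there is no baseline.* Screening takes a medical history and reviews the record, and section 15.1 records significant screening abnormalities as preexisting conditions. What is missing is a measured glucose and a tracing.
- *That the MTD would be wrong.* Escalation turns on Grade 3 or higher toxicity, and the documents give no rate from which any effect could be worked out.

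What the reply does not answer is the symptom-free case. History records known disease, questioning finds symptoms, and the provision in Appendix A for extra laboratory tests concerns repeats of evaluations on a panel without glucose. Nor does the reply explain why a simple analyte is left off a sample that is already taken.

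**Conclusion.** The point holds in a limited form. Glucose and ECG are scheduled at 0 of 5 time points, although section 10 names effects on both from the disease and from the drug class. Symptom-free changes are not systematically detected and have no measured pre-dose value. Known or symptomatic disease remains covered. The consequence is a gap in what the primary safety summary can support, not a demonstrated error in escalation or in the MTD.

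The schedule and visit sections are present in full, so the gap is not an effect of removed pages. The size of the loss cannot be stated, because the documents give no rate for either kind of event.

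The two halves deserve different treatment. Glucose is a worthwhile, low-cost improvement, on the assumption that it can be run on the sample already drawn for chemistry. An ECG would be an additional procedure, and given the stated monitoring focus the documents do not make a case for requiring one. For rhythm, a stated limitation is enough.

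**What to change.** **Glucose.** Add it to the chemistry list in sections 7.4 and 9.1 to 9.4 and in Appendix A, footnote c, and say that the Visit 4 panel in section 9.5 includes it. Name it among the key laboratory results in section 14.2, summarised by CTCAE grade with the pre-dose value as baseline. That value should come from the Day 1 sample, or from the combined Screening and Visit 1 sample, because historical results of up to 28 days are accepted for study entry and may not include glucose.

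*Cost:* one analyte on existing draws, four or five per subject and at most 120 results in all. The downside is small but real: non-fasting values are noisier, and some will need follow-up, which may mean a further sample.

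**ECG.** Reconcile section 10 with Appendix A in wording. State that rhythm and ECG effects are captured only through symptoms, examination or unscheduled tests, and that the trial cannot conclude on symptom-free ECG changes. Repeat this limitation when the results are reported.

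*Cost:* two or three sentences and no added procedure.
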